2. INTRODUCTION AND STUDY RATIONALE

Evidence supporting the idea that microemboli accompany transient ischaemic attacks (TIAs), amaurosis fugax and stroke is rapidly accumulating and it is now generally accepted that such microemboli originate at the site of vascular stenosis (Sitzer et al., 1995, Siebler et al., 1992). These microemboli are made up of platelet aggregates that form by two major mechanisms. Firstly, when atherosclerotic plaques ulcerate and rupture, subendothelial tissues expose factors of high platelet-activating potential. Secondly, platelet adhesion and activation at the site of stenosis is greatly facilitated by increased shear stress resulting from blood flow turbulences in atherosclerotic vasculature (Lassila et al., 1990).

In patients with symptomatic stenoses of the internal carotid artery (ICA), a large number of microemboli enter the cerebral circulation, thereby potentially producing a symptomatic clinical event. They can be detected by Transcranial Doppler (TCD) in the form of characteristic microembolic signals (MES) (Ringelstein et al. 1998). Several studies have demonstrated that the incidence of MES is a potent prognostic factor for prediction of future strokes and TIAs in patients with systematic stenosis, i.e. the risk being 8 to 31 fold higher for MES positive patients than for MES negative patients (Valton et al., 1998, Molloy et al. 1999, Siebler et al., 1995).

Patients suffering a TIA or stroke are at 30-35 % risk of suffering recurrent stroke within the next 5 years and are advised to undergo vascular surgery in order to reduce the risk of future brain infarction (NASCET Collaborators 1991). In addition to surgical carotid endarterectomy (CEA), administration of antiplatelet agents also favours event free survival and reduces MES frequency in patients undergoing carotid endarterectomy (CEA) (Molloy et al., 1998) and in patients with symptomatic carotid stenosis (Goertler et al., 1999).

Although current antiplatelet agents do reduce the risks for recurrent stroke during and after CEA, their use is associated with potentially life-threatening bleeding complications. It is therefore highly desirable to develop novel therapeutic strategies that selectively inhibit thromboembolisation at the site of vascular stenosis whilst not compromising systemic haemostasis.

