6.3. Supportive Care

The accompanying medication will encompass the entire spectrum medication for treatment of carotid stenosis, TIA, amaurosis fugax and stroke in accordance with the corresponding guidelines. The investigation plan will in no way present restrictions in this sense, see section 5.2.2 for prohibited treatments. Most importantly, this clinical trial will not delay or hinder carotid artery desobliteration. Any required change of concomitant medication in accordance with clinical needs will be documented.

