7.1.2. Visit 2: Treatment

- Physical examination/ vital signs
- Review of concomitant medication
- The trial participant will be given the opportunity to report adverse events (AE) spontaneously, a general prompt will also be given, all adverse events will be followed up until resolution or stabilisation
- Assessment of neurological status (MRS, Barthel Index, NIH Stroke Scale)
- Before administration of study medication, in vitro bleeding time PFA100 / PFA200 and platelet aggregation assay (response to collagen, ADP and TRAP)
- Before administration of study medication, a blood sample for detection of anti-Revacept antibodies will be collected (negative control)
- Pharmacokinetic blood sampling (for approximately 20 % of patients)
 - **t0** prior to IMP administration,
 - **t 0.5h** 30 mins (\pm 5 mins) after start of IMP infusion
 - **t 6h** 6 h (\pm 1 hr) after start of IMP infusion
- **Administration of study medication** will be performed by intravenous infusion for 20 minutes; the time of administration must be recorded.

7.1.3. Visit 3: 24 hrs after treatment (between 2 hrs and 46 hrs after treatment)

- Physical examination/ vital signs
- Review of concomitant medication

- Assessment of AEs
- TCD RECORDING
- ECG examination
- clinical biochemistry, clinical haematology (incl. assessment of bleeding according to RE-LY study group criteria), coagulation and urinalysis
- in vitro bleeding time PFA100 PFA200 and platelet aggregation assay (response to collagen, ADP and TRAP)
- Pharmacokinetic blood sampling (for approximately 20 % of patients)
 - **t24h** 24 hours (\pm 4 hrs) after start of IMP infusion

7.1.4. Visit 4: CEA / intervention (3 days after treatment, -69 hrs / + 5 days)

- Physical examination/ vital signs
- Review of concomitant medication
- Assessment of AEs
- in vitro bleeding time PFA100 /PFA200 and platelet aggregation assay (response to collagen, ADP and TRAP)

THEREAFTER CEA SURGERY OR OTHER INTERVENTIONS CAN BE PERFORMED WITHOUT DELAY

- Pharmacokinetic blood sampling (for approximately 20 % of patients)
 - **T3d** 3 days (\pm 48 hrs) after start of IMP infusion

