7.2.7. Transcranial Doppler

Central Analysis & Test Run

Each study centre shall send a test dataset to the central core laboratory prior to starting patient recruitment. The core lab will notify the study centre and sponsor of successful completion of a test run. TCD recordings are to be sent to the following core lab for central analysis:

PD Dr. med. [name]
Facharzt für Neurologie
[name]
[name]
[contact]
[contact]

Central analysis will be performed for both TCD datasets recorded for each patient enrolled (i.e. visit 1 and 3).

There is no need for local analysis of TCD recordings. Both TCD recordings are analysed centrally only.

MES detection by TCD

TCD recordings will be made from the middle cerebral artery (MCA), via the trans-temporal route. Each TCD assessment is recorded for one hour as specified below.

All TCD recordings must be performed under similar conditions, i.e.:

- Same apparatus
- Same position of patient
- System settings

All recordings shall be performed with a DWL TCD machine with single-depth 2-MHz transducers. Standard settings should be used. Machine settings shall be adapted to harmonised consensus guidelines (Ringelstein et al., 1998) and agreed upon by all study centers. For TCD recording, patients are to be placed in a sitting or supine position. The MCS will be identified via transtemporal window and a transducer will be attached using a

standard headset. TCD signals are recorded for one hour. The total number of MES per hour will be analysed.

Spectral display and audio signals will be monitored acoustically and visually online by an experienced observer during all recordings. Audio and visual signals will be recorded onto suitable storage media for central analysis.

MES will be identified visually as predominantly unidirectional short-duration intensity increase accompanied by characteristic acoustic clicking, chirping or moaning sounds. A previously agreed threshold will be set at all participating study centres following validation by analysis of standard reference tapes. MES intensity will be measured in dB and be calculated as the ratio of peak intensity of MES divided by the intensity of the background signal. The same algorithm will be used throughout the study. Central offline analysis of all recordings will be performed using the same machine and same algorithm.

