### 8.4.1 Reduction of incidence of preoperative microembolic signals

This endpoint is to evaluate whether the rate of patients with incidence of preoperative microembolic signals (MES) was reduced (from Visit1 to Visit 3). Compared will be patients who have been treated with Revacept plus antiplatelet therapy (aspirin or clopidogrel) versus antiplatelet therapy alone (placebo) prior to carotid endarterectomy (CEA). MES data from the central reading lab ([name], Münster) are evaluated.

The evaluation will be performed using a two-sided test of superiority. Groups will be compared for the combined centers using Fisher's exact test.

The sequence of a priori defined hypotheses, with  $\pi$  rate of patients with MES V3 < MES V1 for the specified group, will be:

1)  $H_{01}: \pi_{\text{Revacept 120 mg}} = \pi_{\text{Placebo}}$  VS.

$H_{A1}: \pi_{\text{Revacept 120 mg}} > \pi_{\text{Placebo}}$

2)  $H_{02}: \pi_{\text{Revacept 40 mg}} = \pi_{\text{Placebo}}$  VS.

$H_{A2}: \pi_{\text{Revacept 40 mg}} > \pi_{\text{Placebo}}$

3)  $H_{03}: \pi_{\text{Revacept 120 mg}} = \pi_{\text{Revacept 40 mg}}$

$H_{A3}: \pi_{\text{Revacept 120 mg}} > \pi_{\text{Revacept 40 mg}}$

4)  $H_{04}: \pi_{\text{Revacept 120 mg + 40 mg}} = \pi_{\text{Placebo}}$  VS.

$H_{A4}: \pi_{\text{Revacept 120 mg + 40 mg}} > \pi_{\text{Placebo}}$

Each hypothesis will be tested using Fisher's exact test.

With the first two and the last of hypotheses the test product for a given dose level or overall will be tested against Placebo. With the third hypothesis the higher dose level of the test product will be compared against the lower dose of the test product.

Statistical Analysis Plan  
Test product: Revacept  
EudraCT number: 2011-001006-10  
Date 10.06.2019

All tests will be interpreted exploratively.

The between group risk difference and its 95% confidence interval (CI) will be estimated for each group comparison.

The prime analysis will be based on the ITT population. The PP population will be used for the supportive analyses.

In a subgroup analysis, only patients will be compared who did not receive any change in the concomitant medication with anti-platelet activity (=rescue medication) between the initial assessment at V1 and the follow-up investigation at V3 / V5.

Additionally the prevalence / rate of patients with microembolic signals (>0) at Visit 3 will be compared in a similar manner as in the hypothesis 1- 4

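### The MES endpoints are labelled preoperative but taken by visit label; the permitted windows let a compliant Visit 3 recording follow the intervention, and no prespecified rule detects or handles this

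*SAP*

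**What the plan says.** SAP 8.4.1, the first efficacy analysis, is to evaluate whether the "rate of patients with incidence of preoperative microembolic signals (MES) was reduced (from Visit1 to Visit 3"; the comparison is of patients treated before endarterectomy. The tested quantity is the proportion of patients whose MES count at Visit 3 is below that at Visit 1. SAP 8.4.2 compares the MES rate between the same two visits under a heading that places it before CEA.

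The timing comes from the protocol, and the SAP study plan repeats it:

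- Protocol 7.1.3 sets Visit 3, the only Doppler examination after treatment, at "24 hrs after treatment (between 2 hrs and 46 hrs after treatment".
- Protocol 7.1.4 sets Visit 4 as "CEA / intervention (3 days after treatment, -69 hrs / + 5 days".
- Protocol 7.2.7: "TCD signals are recorded for one hour".
- Protocol 7.1.4, after its list of Visit 4 procedures: "THEREAFTER CEA SURGERY OR OTHER INTERVENTIONS CAN BE PERFORMED WITHOUT DELAY". The Doppler recording is not on that list.
- Protocol 6.3: "this clinical trial will not delay or hinder carotid artery desobliteration".

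Three parts of the SAP might have dealt with a recording made after the intervention, and none does. The major deviations in 7.2 and Table 6-1 do not name it. The missing-value rules in 7.3 and 8.4.1 carry the last observation forward for patients who dropped out before the visit, which makes them non-responders. The responder definition itself refers to visits, not to the time of the intervention.

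**The concern.** The protocol's introduction states that "such microemboli originate at the site of vascular stenosis". On that reasoning, a recording made after the stenosis has been treated reflects the intervention as well as the study drug. It is then not the quantity that 8.4.1 and 8.4.2 are named for.

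The SAP already guards against a similar disturbance. It plans a subgroup of patients whose antiplatelet medication did not change between Visit 1 and the follow-up examination. It has no counterpart for the intervention.

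This endpoint is listed first among the efficacy endpoints, and the Visit 3 recording is the only post-treatment efficacy examination scheduled before the intervention. If some Visit 3 recordings are postoperative, the comparison is diluted when the share is equal across arms, and shifted when it is not. A decision on such patients made after unblinding would be open to criticism.

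**Working it through.** **1. Reproduce the stated window.** The protocol's schedule table gives Visit 3 as T + 24 h ± 22 h: 24 − 22 = 2 h and 24 + 22 = 46 h. This matches the text of 7.1.3; the width is 44 h.

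**2. Intervention window.** Three days is 72 h: 72 − 69 = 3 h and 72 + 120 = 192 h; the width is 189 h. Protocol and SAP agree.

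**3. Overlap.** min(46, 192) − max(2, 3) = 43 h. That is 43/44 = 97.7% of the Visit 3 window and 43/189 = 22.8% of the intervention window. A one-hour recording is certain to finish by the earliest permitted intervention only if it starts at exactly 2 h. A patient operated on at 12 h and recorded at the nominal 24 h meets both windows, triggers no listed deviation, and is analysed as preoperative.

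**4. What this does not give.** The overlap is not a frequency. The nominal times are 24 h and 72 h, and the documents report no actual timings.

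**5. How the handling of such recordings moves the result.** The documents give no inputs for this, so the following are assumptions chosen for illustration:

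- a proportion p = 0.30 of patients have MES at Visit 1;
- q = 0.54 of these show a lower count at Visit 3 by chance alone, with no drug effect;
- a share f of Visit 3 recordings is postoperative, independent of MES status, and these recordings show no MES.

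Responder rate under three handlings:

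- as labelled: p × [(1 − f) × q + f]
- postoperative recordings through LOCF (non-responders): p × (1 − f) × q
- postoperative recordings left out: p × q

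| Handling | f = 0.20 | f = 0.05 | Difference with no drug effect |
|---|---|---|---|
| As labelled | 0.30 × (0.80 × 0.54 + 0.20) = 19.0% | 0.30 × (0.95 × 0.54 + 0.05) = 16.9% | +2.1 points |
| Through LOCF | 0.30 × 0.80 × 0.54 = 13.0% | 0.30 × 0.95 × 0.54 = 15.4% | −2.4 points |
| Left out | 0.30 × 0.54 = 16.2% | 16.2% | 0 |

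Among patients with MES at Visit 1 the first two rows are 63% against 56%, and 43% against 51%. If the intervention provokes MES, so that these patients never show a lower count, the as-labelled result equals the LOCF row and the sign reverses.

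**6. Equal shares.** With f = 0.10 in both arms, both as-labelled rates are 0.30 × (0.90 × 0.54 + 0.10) = 17.6%, so there is no false difference. A real drug effect that raises q to q′ appears as p × (1 − f) × (q′ − q), which is one tenth smaller at f = 0.10.

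**The case against.** The strongest reply is that the order is built into the design. The intervention is Visit 4 and follows Visit 3 by number, the endpoint is named preoperative, and 8.4.2 says before CEA. The lower limits fit this too: a recording begun at 2 h ends at 3 h, exactly when the intervention window opens. This stands as evidence of intent, and a reader should not infer that the plan means to use postoperative recordings. But an intended order is not a check. The analysis follows the visit label, and the protocol states that it will not hold surgery back.

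A reader might also infer from the 43 of 44 h that most recordings are at risk. The documents do not support that: the figure compares permitted windows, and the share affected is unknown.

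Nor do they support a claim of substantial bias. In a blinded randomised trial an uneven share would arise mainly by chance. With 50 per arm, 20% against 5% is about 10 patients against 2 or 3 (Fisher's exact p about 0.03 to 0.07), an unlikely split. Even then the shift is 2.1 points, about one patient in an arm of 50, in a study that the SAP declares exploratory.

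It would also be wrong to call MES the only efficacy information before surgery, since SAP 8.4.5 summarises clinical events before CEA as well.

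The blinded data review could catch such cases, because the list of major deviations in SAP 7.2 is expressly open-ended. That is the right place for the check, but nothing prespecifies it, and classification as a deviation would affect only the per-protocol set, not the first-line ITT analysis.

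**Conclusion.** The point holds as a gap between the endpoint's definition and its implementation. Followed literally, the plan can count a postoperative recording as preoperative in 8.4.1 and 8.4.2, and no prespecified rule finds or handles it. This rests on the stated windows and on the absence of a rule, not on any assumed frequency.

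The size of the effect cannot be derived from the documents. If the intended order was always kept, nothing changes. The illustration shows only that the handling matters: under deliberately uneven shares the as-labelled analysis is off by 2.1 points, while treating the same recordings as missing under the existing LOCF rule is off by 2.4 points in the opposite direction. Simply declaring such recordings missing is therefore not a remedy. Leaving them out gives no false difference in the illustration because the timing of the intervention was assumed unrelated to MES. If that fails, leaving them out is itself a selection on a post-randomisation event, which is why sensitivity analyses are needed.

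**What to change.** Change the SAP only, before unblinding. It describes recruitment in the past tense, so rewording the protocol's visit instructions would probably come too late to matter.

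- At the blinded data review, compare the date of each Visit 3 recording with the date of the intervention, using clock times where they were recorded. Report by arm the number of Visit 3 recordings made after the intervention. State in advance how same-day cases without times are classified.
- In 8.4.1 and 8.4.2, specify that the main analyses use only recordings made before the intervention, and that later recordings are not put through the LOCF/non-responder rule.
- Add two sensitivity analyses: (a) all Visit 3 recordings as labelled; (b) patients with a post-intervention recording counted as non-responders.

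The sponsor should reconcile the visit windows with the preoperative wording. No change to the timing of surgery is proposed.

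The cost is some SAP text and one data check. The check may be limited to dates: the CEA items listed in protocol 7.2.3 include durations but no start time, 7.2.7 mentions no recording time, and the CRF is not among the documents. The statistical downside is that a few patients may leave the main MES analysis, a small departure from full ITT that the two sensitivity analyses make visible. If no such recording exists, one sentence in the blind review report settles the matter.

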6.1.7. Randomisation

Patients will be assigned to a treatment group by web-based online randomisation. Each patient will be allocated to one of the three treatment arms using a minimised randomisation method in order to balance potential prognostic factors between individual treatment arms. The following stratification factors will impact on treatment allocation:

- (1) Patient has received anti-platelet therapy with aspirin or clopidogrel prior to screening
 - No
 - Yes
- (2) Patient has received statin therapy prior to screening
 - No
 - Yes
- (3) Degree of carotid stenosis (ECST criteria)
 - 50-70%
 - > 70%

Once a patient is found to fulfil all eligibility criteria of the study the patient's identification number and details on concomitant medication are submitted to a web-based online randomisation program accessible at:

<https://www.randomizer.at/random/web/login.php>

All trial staff involved in patient randomisation will receive their log in data for the program after a short introduction to the system. In order to randomise a new patient, select "randomise" in the control panel on the left, enter the patient number (numeric format, including centre specific prefix, e.g. 01-005), select the applicable stratification

factors and click "randomise".

In case a reduced set of medication kit boxes is available at the study centre (e.g. due to damage or expiry of trial medication), you may tick option "reduced set of treatments", select "next", highlight all **unavailable** kit box numbers and then click on "randomise".

After successful randomisation of a patient, the web-based online system will send a confirmation email to the person who randomised the patient which contains the patient-specific random kit box number. This confirmation is to be printed, dated, signed and filed in the Investigator Site file.

Please check the number of remaining IMP kit boxes after each patient enrolment and make sure to request additional supplies as soon as less than 10 kit boxes remain, or earlier, in case of high recruitment rates.

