## **3.3 Sample size**

Primary sample size estimation was conducted based on the CARESS study results (Markus et al., 2005). 50 patients should be allocated to each treatment arm. Due to low incidence of MES (high screening failure rates) study design was changed to exploratory study (Version 8 of the study protocol).

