### **6.2 Full Analysis Set**

For efficacy, all subjects who have had at least one dose of medication will be included in the ITT analysis. The ITT analysis is defined as the first line efficacy analysis.

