### **8.2.8 TCD**

The result of the TCD central assessment ([name], Münster) is a key element for the efficacy analysis of the study, see 8.4

The technical possibility to perform TCD (sufficient bone window) determines whether a patient is eligible for the study.

- TCD assessment was successful

Due to high rate of no microembolic signals we abandoned the criterion that if no microembolic signal was detected during the recording period then the patient was rated not eligible during the course of the study. In the further course of the study patients were included irrespective whether they present with microemboli or not.

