Missing values for the primary analyses at Visit 3 will be imputed by the last observation carried forward approach. This means patients who dropped out before Visit 3 will be counted as non-responder.

An additional analysis of the first endpoint will be performed including the factor center as a stratum. Fisher's exact test will be performed for each stratum and meta-analysis approach will be chosen. Centers with less than 3 patients will be combined into a 'small number of patients' combined stratum.

Individual center results will be presented in a graphical overview with risk differences and their confidence intervals.

**In case of heterogeneities in the baseline parameters**, sensitivity analyses will be performed for the first endpoint using Fisher's exact test and by including the respective parameter as a stratum (binary, ordinal or categorical data). For continuous data these data will be transformed into classes before used as stratum.

A meta-analysis approach will be chosen to pool the stratum dependent results and to investigate for heterogeneity in the strata (e.g. Whitehead, 2003).

The following baseline parameters will be used for the analysis of heterogeneity:

- Demographics
  - Age
  - Height
  - Weight
  - Ethnic origin
  - Gender
  - Hormone status
- Anamnesis – Medical history
  - Number of patients with previous diseases and surgeries
- Vital signs
  - systolic and diastolic blood pressure (right and left arm)

- Physical examination
  - Abnormal findings of assessment of heart, lung, abdomen and oedema (Yes/No)

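### No efficacy test in SAP 8.4.1 to 8.4.6 adjusts for baseline outcome or a minimisation factor; patients with no MES at Visit 1 dilute the V3 < V1 comparison, at a cost in precision

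*SAP*

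**What the plan says.** Protocol 6.1.7 minimises allocation on prior antiplatelet therapy, prior statin therapy and degree of stenosis, "in order to balance potential prognostic factors between individual treatment arms".

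The planned efficacy tests are:

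- **SAP 8.4.1:** response is MES at V3 below MES at V1, and "Groups will be compared for the combined centers using Fisher's exact test". The ITT population comes first: "The ITT analysis is defined as the first line efficacy analysis" (SAP 6.2). A second comparison follows: "Additionally the prevalence / rate of patients with microembolic signals (>0) at Visit 3 will be compared".
- **SAP 8.4.2:** ANOVA of change and percent change in MES, with Wilcoxon if normality fails.
- **SAP 8.4.3:** ANOVA of total NIHSS by visit.
- **SAP 8.4.4:** ANOVA of change and percent change in DWI lesions, and Fisher tests for any, new and reduced lesions at V5.
- **SAP 8.4.5:** Fisher tests of clinical events.
- **SAP 8.4.6:** Cochran-Mantel-Haenszel (CMH) stratified by rescue medication, a post-randomisation variable.

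SAP 8.4.1 also plans an additional analysis with centre as stratum. If baseline heterogeneity is found, "sensitivity analyses will be performed for the first endpoint using Fisher's exact test and by including the respective parameter as a stratum". No threshold for heterogeneity is given. The list covers demographics, medical history, blood pressure and physical examination; it contains neither V1 MES nor a minimisation factor.

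On entry, SAP 8.2.8 says: "Due to high rate of no microembolic signals we abandoned the criterion that if no microembolic signal was detected during the recording period", and then "In the further course of the study patients were included irrespective whether they present with microemboli or not". SAP 3.3 adds: "Due to low incidence of MES (high screening failure rates) study design was changed to exploratory study".

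**The concern.** Baseline outcome enters only through how some endpoints are defined: change, percent change, new or reduced lesions, and V3 < V1. It does not enter at all for NIHSS by visit, MES prevalence at V3 or the lesion rate at V5, although the earlier value is scheduled for each.

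The sharpest case is V3 < V1. A count of 0 at V1 cannot fall, so such a patient is a non-responder in every arm whatever the drug does. Including these patients shrinks the risk difference and adds between-patient variation that V1 status would explain. The DWI endpoint of fewer lesions at V5 than at V1 has the same structural zero. Percent change is undefined when the baseline is 0, and the SAP gives no convention for it.

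The stake is not a false claim. In an exploratory trial the estimates and their intervals are the product, and the Protocol synopsis foresees combining these data with future studies. A risk difference that depends on an unspecified share of V1-negative patients is hard to carry forward.

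**Working it through.** **Inputs.** From the documents: 50 per arm (SAP 3.3), two-sided Fisher test and 95% CI (SAP 8.4.1). The only sample-size check possible is 3 × 50 = 150, because no rates, power or alpha are given. Assumed: alpha 0.05; V1 MES prevalence q, described only as low, varied from 10% to 90%; response among V1-positives 40% on placebo and 80% or 60% on Revacept.

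**Dilution.** If r is the response rate among V1-positives, an arm's overall rate is q × r. The expected risk difference is q × (r_active − r_placebo). With 80% v 40%, that is 0.2 × 40 = 8 points at q = 20% and 0.5 × 40 = 20 points at 50%, against 40 points in V1-positives.

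**Variance.** Times n, the per-arm variance is qr(1 − qr) unstratified and qr(1 − r) given V1 status. At q = 0.2 with 0.4 v 0.8:

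- unstratified: 0.08 × 0.92 + 0.16 × 0.84 = 0.208
- given V1 status: 0.08 × 0.6 + 0.16 × 0.2 = 0.080, ratio 0.080/0.208 = 0.38
- adding q(1 − q)d²/2 = 0.16 × 0.16/2 = 0.0128 for chance in the number of V1-positives: 0.0928/0.208 = 0.45

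The ratio goes to 1 as q goes to 1.

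**Exact power.** The V1 = 0 stratum has no responders, so an exact test stratified by V1 status equals Fisher's test within V1-positives. V1-positives per arm are Bin(50, q), and responders are binomial within them. Power is shown for all patients v V1-positives.

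| V1 prevalence | 80% v 40% | 60% v 40% |
|---|---|---|
| 10% | 4 v 12% | 1 v 4% |
| 20% | 14 v 34% | 5 v 9% |
| 30% | 26 v 53% | 8 v 14% |
| 50% | 51 v 80% | 15 v 24% |
| 70% | 77 v 92% | 24 v 33% |
| 90% | 95 v 97% | 38 v 42% |

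Under the null (40% v 40%), rejection is 0.4 to 3.1% in all patients and 1.4 to 3.6% in V1-positives, so the gain is not error inflation.

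**Other endpoints, for scale.**

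- *NIHSS.* The variance ratio of ANCOVA to follow-up-only ANOVA is 1 − ρ²: 0.75, 0.51, 0.36 and 0.19 at ρ = 0.5, 0.7, 0.8 and 0.9.
- *Absolute change scores.* The ratio of ANCOVA to change-score ANOVA is (1 + ρ)/2, which is 0.55 to 0.95 for ρ = 0.1 to 0.9.
- *MES counts, simulated* (rate ratio 0.4, 50% prevalence, three assumed V1–V3 relations from weak to proportional). Change-score ANOVA has 22, 25 and 27% power against 67, 66 and 56% for ANCOVA. A separate run gave 33, 46 and 64% for the planned percent-change ANOVA in V1-positives, against 62, 64 and 53% for ANCOVA. When V3 is proportional to V1, percent change does better.
- *Minimisation factors alone* (odds ratio 2 each): about −1 to 3 power points.

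**The case against.** The strongest reply is that the Protocol plans no formal hypothesis testing, the SAP interprets every test exploratively, and the planned tests are valid as they stand. All of that is right, and it limits the point to lost precision. The SAP nevertheless lists four hypotheses in sequence with risk differences and 95% CIs, so precision still matters.

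Three further replies also stand:

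- The plan is not blind to baseline. Change scores use it, and percent change, being undefined at 0, is in effect a comparison within V1-positives unless a convention is added. The planned Wilcoxon fallback also recovers a little for skewed counts.
- Every rate is assumed, and with a modest effect the gain is small.
- The V1-positive comparison answers a different question from the ITT one, and adding it does not narrow the ITT interval.

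A reader might infer that V3 < V1 suffers the largest loss of all the endpoints. The documents do not support that ranking: they give no prevalence, response rate or correlation, and NIHSS or absolute MES change loses more under some of the assumptions above. Nor do they support the inference that leaving out the minimisation factors does material harm; the calculated effect of including them is close to nil.

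**Conclusion.** The omission and the structural zero follow from the text. No efficacy test conditions on baseline outcome or on a minimisation factor, and patients with V1 MES = 0 are counted in a comparison in which they cannot respond.

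The loss for V3 < V1 can be large: about 20 to 28 power points at 20 to 50% prevalence if the effect in V1-positives is 80% v 40%. It is at most about 9 points at 60% v 40%, and it fades as prevalence approaches 100%. The low MES incidence that the SAP reports makes the low-to-moderate range the relevant one, but the actual prevalence is not given. Early patients enrolled under the MES requirement would raise it.

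This is a cheap improvement in precision and interpretability, not the correction of an invalid analysis.

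**What to change.** Settle the following in the final SAP, which SAP 1 places in the Blind Review Report before the blind is broken:

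- **V3 < V1.** Keep the ITT Fisher test and risk difference as first line. Add a pre-specified comparison stratified by V1 MES (0 / >0), reported as the effect within V1-positives with its own risk difference and 95% CI. Do the same for reduced DWI lesions, by V1 lesion status.
- **V3 MES > 0 and V5 lesion yes/no.** CMH stratified on baseline status.
- **NIHSS total at V5 and V6.** ANCOVA on the V2 score, only where that score was recorded before infusion, with rank ANCOVA as sensitivity. Protocol 7.1.2 lists NIHSS at Visit 2 without saying that it precedes dosing.
- **MES and DWI counts.** ANCOVA of the follow-up value on the V1 value in place of absolute change-score ANOVA, with rank ANCOVA as sensitivity. Keep percent change, and state that it applies only to patients with a baseline above 0.
- **Minimisation factors.** Optional sensitivity covariates. Do not cross them with baseline status: 2⁴ = 16 cells average 100/16 = 6.25 patients in a pairwise comparison.

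The cost is SAP text and modest programming on variables already scheduled for collection. There are two downsides. The V1-positive estimate is conditional and may rest on few patients (0.3 × 50 = 15 per arm at 30% prevalence). The additions also produce more exploratory p-values across the four contrasts.
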